### **7.6.1 Overall Adverse Events**

#### **Summary:**

AEs and drug-related AEs will be tabulated by descending frequency of SOC and descending frequency of PT within each SOC, unless specified otherwise.

- Overall summary of any AEs by worst CTC grade (grade 1, 2, 3, 4, 5, unknown) presented by SOC/PT
- Overall summary of drug-related AEs by worst CTC grade (any grade, grade 3-4, grade 5) presented by SOC/PT.
- Overall summary of any non-serious AEs presented by PT. This table will be restricted to events with an incidence greater or equal to 5% in any dose+dose regimen group for all treated subjects (total).

#### **Listing:**

All recorded Adverse Events occurring in the pre-treatment, on-treatment, and post treatment period will be listed.

### **7.6.2 Deaths**

#### **Summary:**

All deaths during the study within 60 days after the last dose of BMS-986148 will be summarized for cause of deaths by treatment.

**Listing:**

All recorded deaths for All Enrolled subjects will be listed.

**7.6.3 Other Serious Adverse Events**

**Summary:**

- Summary of SAEs by worst CTC grade (grade 1, 2, 3, 4, 5, unknown) presented by SOC/PT.
- Summary of drug-related SAEs by worst CTC grade (any grade, grade 3-4, grade 5) presented by SOC/PT.

**Listing:**

By-subject SAE listing will be provided for the All Enrolled Subjects.

**7.6.4 Adverse Events Leading to Discontinuation of Study Therapy**

Adverse events leading to study drug discontinuation are AEs with action taken = “Drug was discontinued”.

**Summary:**

- Overall summary of AEs leading to discontinuation by worst CTC grade (grade 1, 2, 3, 4, 5, unknown) presented by SOC/PT.
- Overall summary of drug-related AEs leading to discontinuation by worst CTC grade (any grade, grade 3-4, grade 5) presented by SOC/PT.

**Listing:**

By-subject AEs leading to discontinuation listing will be provided.

**7.6.5 Multiple Events**

Analyses that take into account the multiple occurrences of a given adverse event will be conducted. In order to prepare these analyses, the CRF data will be processed according to standard BMS algorithms in order to collapse adverse event records into unique records based on the preferred term. This data will be presented as the rate per 100 patient-years of exposure. This analysis will take into account all on-treatment events (allowing more than 1 event per subject) and the total duration of exposure. The patient-years exposure will be computed as the sum over the subjects’ exposure expressed in years where the duration of exposure is defined as

- Date of last dose of study treatment - date of first dose of study treatment + 7 (for QW dosing regimen) or + 21 (for Q3W dosing regimen) days, for subject who are off study treatment and were followed at least 60 days after last dose of study medication.
- Last known date alive- date of first dose of study medication +1, for subjects who are still on-treatment or who are off study treatment and were followed less than 60 days after last dose of study medication.

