#### **3.1.2 Dose Expansion (Part 2)**

The purpose of the cohort expansion will be to assess preliminary antitumor efficacy, expanded safety experience, and PD effects of BMS-986148. Additional subjects will be treated after the completion of Part 1A and/ or Part 1B, at the MTD, or at an alternative dose below MTD as agreed upon by the BMS Medical Monitor and investigators. Part 2 can begin before the completion of Part 1B as the Q3W dosing regimen is the intended regimen for Part 2. However, if the aggregate PK and safety data indicate similar safety but higher cumulative exposure with the QW dose schedule, this schedule may also be evaluated in Part 2 in an additional cohort of 25 to 26 subjects, once the MTD or a tolerated dose below the MTD is identified in Part 1B. Treatment doses in the cohort expansion groups will not exceed the MTD.

Five expansion cohorts will be restricted to these tumor types 1) mesothelioma 2) pancreatic 3) ovarian 4) NSCLC, and 5) gastric cancer. Enrollment in cohort expansion will be determined by the mesothelin expression of the archived tumor sample (or fresh tumor sample if archived sample is not available).

The enrollment in each expansion cohort will be guided by a Simon 2-Stage design framework (see [Table 8.1-1](#)) exploring efficacy in the following 2 populations: [REDACTED]

Anti-tumor activity will be assessed initially in approximately 12 to 15 evaluable subjects per tumor type (Stage 1) treated in each monotherapy cohort, with the option to stop enrolling in a cohort without an initial anti-tumor activity signal. The number of subjects needed for the Stage 1 review is guided by a Simon 2-Stage design as shown in Table 8.1-1 below for each tumor type with futility boundaries as follows: after Stage 1, if none of the first 15 evaluable subjects in the gastric or pancreatic cohorts, if  $\leq 2$  of the first 12 with mesothelioma, or  $\leq 1$  of the first 14 with NSCLC or ovarian cohort demonstrate clinical activity, enrollment in the cohort meeting criteria may be stopped for this population.

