- h Subjects with SD, PR, or CR at the last clinical follow-up visit should undergo tumor assessment via CT/MRI scans at least every 3 to 4 months during the Survival Follow-up ([Section 8.3.2.2](#)) phase until progression.
- i Subject status will be assessed by either a clinic visit or telephone contact every 12 weeks ( $\pm$  2 weeks) until the last treated subject has been followed for 2 years from his/her first date of treatment. The nature and start dates of any new therapies during this period should be recorded. Only information related to subjects' survival and the start date of any subsequent therapies will be collected at these telephone contacts. Subjects will be permitted to receive other anti-cancer therapies, including investigational agents, during this follow-up period once the 60-day follow-up visit is completed.
- C: cycle; CBC: complete blood cell (count); CR: complete response; CT: computed tomography; D: day; ECG: electrocardiogram; EOT: end of treatment; MRI: magnetic resonance imaging; PE: physical examination; PK: pharmacokinetics; PR: partial response; Q3W: every 3 weeks; SAE: serious adverse event; SD: stable disease.

**Table 5.1-4: Screening and Cycle 1, Part 1B (Weekly Dosing BMS-986148 Monotherapy Dosing / 28 Day Cycle) Procedural Outline (CA008002)**

Procedure a	Pre-Screening	Screening Visit D-28 to D-1	C1D1	C1D2	C1D4 b	C1D8	C1D15	C1D22	Notes
Eligibility Assessments									
Informed Consent		X							A subject is considered enrolled only when a protocol specific informed consent is signed. In Part 2, if allowed by institutional practices, sites are encouraged to use a pre-screening consent for the mesothelin-expressing tumor analysis. Other screening procedures should not be done before the mesothelin-expressing tumor analysis is available for the determination of subject eligibility.
Inclusion/Exclusion Criteria		X							
ECOG		X	X						
Medical History		X							Also include any toxicities or allergy related to previous treatments. Smoking history for all subjects.
Prior Treatments		X							Including prior cancer treatment regimens and medications administered within 4 weeks of dosing.

**Table 5.1-4: Screening and Cycle 1, Part 1B (Weekly Dosing BMS-986148 Monotherapy Dosing / 28 Day Cycle) Procedural Outline (CA008002)**

Procedure a	Pre-Screening	Screening Visit D-28 to D-1	C1D1	C1D2	C1D4 b	C1D8	C1D15	C1D22	Notes
Safety Assessments									

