**7.6 Safety**

Analysis of safety will be based on All Treated Subjects and presented by dose, dose regimen, and overall (if appropriate).

Adverse events (AEs) will be coded according to the most current version of MedDRA and be graded using the NCI Common Terminology Criteria for Adverse Events (CTCAE) version 4.03. Drug-related AEs are those events with relationship to study drug “Related” as recorded on the CRF. If the relationship to study drug is missing, the AE will be considered as drug-related.

Listing of adverse events will include all enrolled subjects as SAEs and deaths are collected pretreatment. Summaries of adverse events will include (1) events occurring from the first dose date to 60 days (inclusive) after the last dose of BMS-986148 for subjects who are off study treatment and (2) all events occurring from first dose date for subjects who are still on study medication.

When reporting adverse events by CTC grade, summary tables will be provided based on the event with worst CTC grade (independent of relationship to study medication). Subjects will only be counted (1) once at the preferred term (PT) level, (2) once at the system organ class (SOC) level, and (3) once in the ‘Total subject’ row at their worst CTC grade, regardless of SOC or PT.

The analysis of laboratory results will be based on All Treated Subjects. Laboratory results will be categorized according to NCI CTCAE (version 4.03) grade. Baseline is defined as the last non-missing measurement prior to the first dosing date and time. Summaries of laboratory results include baseline and (1) post-baseline results up to 60 days (inclusive) after the last dose of BMS-986148 for subjects who are off study treatment and (2) all available post-baseline results for subjects who are still on study medication.

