**Summary:**

The following summary tables will be provided:

- Total number and rate (exposure adjusted) of occurrences for all AEs occurring in at least 5% of the subjects treated in any dose + dose regimen group.

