## 8 CONVENTIONS

In general, EmBARC standard time windowing, imputation rules, and counting rules will be applied.

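### SAP 7.6.5 computes patient-years by two rules that do not meet at 60 days of follow-up; against the SAP 7.6 event window, the first is 40 (Q3W) or 54 (QW) days short per subject

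*SAP*

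**What the plan says.** SAP 7.6.5 plans a rate per 100 patient-years that allows several occurrences of an event in one subject. Person-time is defined by two rules.

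- **Rule 1**, for subjects off treatment and followed at least 60 days after the last dose: "Date of last dose of study treatment - date of first dose of study treatment + 7 (for QW dosing regimen) or + 21" days, where 21 applies to Q3W.
- **Rule 2**: "Last known date alive- date of first dose of study medication +1, for subjects who are still on-treatment or who are off study treatment" with less than 60 days of follow-up.

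The events counted are called on-treatment events, a term 7.6.5 does not define. The parent section, SAP 7.6, states the only window for adverse event summaries. For subjects off treatment it takes "events occurring from the first dose date to 60 days (inclusive) after the last dose of BMS-986148"; for the others, "all events occurring from first dose date for subjects who are still on study medication". The planned output is "Total number and rate (exposure adjusted) of occurrences for all AEs occurring in at least 5% of the subjects treated", by dose and dose regimen. SAP 8 adds that, in general, "EmBARC standard time windowing, imputation rules, and counting rules will be applied".

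**The concern.** An exposure-adjusted rate is meaningful only if events and person-time cover the same interval. Here the denominator changes definition at 60 days of follow-up, while the event window in SAP 7.6 does not change. Rule 1 stops one dosing interval after the last dose, although events are counted to day 60. Rule 2 runs to the last known alive date. A subject observed for longer can therefore contribute less person-time than the same subject observed for a shorter period.

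The rate in each dose and regimen group would then depend on how many of its subjects reach 60 days of follow-up. Groups with more early deaths or losses would get a different denominator, so the distortion need not cancel between groups. The terms +7 and +21 also separate QW from Q3W even when events and dosing dates are the same.

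**Working it through.** The documents give no patient-years total or event rate, so there is no stated figure to reproduce. The check is day-count arithmetic on the SAP formulas.

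**Inputs**

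- T = days from first to last dose. The values 42, 84 and 168 are illustrative assumptions, not taken from the documents.
- d = days followed after the last dose. The last known alive date is assumed to be the end of follow-up.
- Rule 1 (SAP 7.6.5, d ≥ 60): T + 21 for Q3W, T + 7 for QW.
- Rule 2 (SAP 7.6.5, off treatment, d < 60): T + d + 1.
- Event window (SAP 7.6, 60 days inclusive), with the same inclusive count as Rule 2: T + 61.

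**Step 1: the join at 60 days.** At d = 59, Rule 2 gives T + 60. At d = 60, Rule 1 gives T + 21 or T + 7. One more day of follow-up removes (T + 60) − (T + 21) = 39 days for Q3W and (T + 60) − (T + 7) = 53 days for QW. Rule 2 exceeds Rule 1 when d + 1 > 21 or d + 1 > 7, that is, for d = 21 to 59 (Q3W) or 7 to 59 (QW). The rules agree only at d = 20 (Q3W) or d = 6 (QW).

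**Step 2: shortfall against the SAP 7.6 window.** 61 − 21 = 40 days (Q3W); 61 − 7 = 54 days (QW). Neither depends on T. For 25 subjects all under Rule 1 this is 25 × 40 / 365.25 = 2.74 or 25 × 54 / 365.25 = 3.70 patient-years.

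**Step 3: effect on the rate, all subjects under Rule 1.** The events are the same, so the inflation is (T + 61) / (T + k), with k = 21 or 7.

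| T | Q3W | QW |
|---|---|---|
| 168 | 229/189 = 1.21 | 229/175 = 1.31 |
| 84 | 145/105 = 1.38 | 145/91 = 1.59 |
| 42 | 103/63 = 1.63 | 103/49 = 2.10 |

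**Step 4: a mix of the two rules.** Let a share p fall under Rule 1 and assume the rest are followed 30 days. The inflation is [p(T + 61) + (1 − p)(T + 31)] / [p(T + k) + (1 − p)(T + 31)].

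| Regimen, T | p = 25% | p = 50% | p = 75% |
|---|---|---|---|
| Q3W, 168 | 206.5/196.5 = 1.05 | 214/194 = 1.10 | 221.5/191.5 = 1.16 |
| Q3W, 42 | 80.5/70.5 = 1.14 | 88/68 = 1.29 | 95.5/65.5 = 1.46 |
| QW, 168 | 206.5/193 = 1.07 | 214/187 = 1.14 | 221.5/181 = 1.22 |
| QW, 42 | 80.5/67 = 1.20 | 88/61 = 1.44 | 95.5/55 = 1.74 |

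**Step 5: regimen comparison.** With equal T and equal events, all under Rule 1, the QW rate divided by the Q3W rate is (T + 21) / (T + 7): 189/175 = 1.08 at T = 168, 105/91 = 1.15 at T = 84, and 63/49 = 1.29 at T = 42.

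**The case against.** The strongest reply is that on-treatment, left undefined in 7.6.5, may mean duration of therapy. Rule 1 is the same expression as duration of therapy in SAP 7.4.1, and the listing in SAP 7.6.1 separates the on-treatment from the post-treatment period. On that reading Rule 1 is right, and the +7 and +21 are an intended credit of one dosing interval. But Rule 2 is then too long for off-treatment subjects, by up to 39 (Q3W) or 53 (QW) days, and rates are biased downward. So the direction of the error depends on the reading; the inconsistency does not. The 60-day window is the better-supported reading: 7.6.5 sits under 7.6, and a split at 60 days has little purpose unless events count to day 60.

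A second reply is that sponsor standards may settle the matter. SAP 8 applies them in general, and 7.6.5 cites a sponsor algorithm for collapsing event records. Those standards are not among the documents, and neither reference displaces a formula that 7.6.5 writes out in full.

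A third reply concerns Rule 2's lack of a cap. Footnote i of Protocol Table 5.1-3 says "Subject status will be assessed by either a clinic visit or telephone contact every 12 weeks", which can put the last known alive date after adverse event collection ended. A subject reached at such a contact may, however, count as followed at least 60 days and so fall under Rule 1. The missing cap matters only if followed means follow-up for adverse events, which the SAP does not say. This part of the concern is narrow.

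Finally, the table is descriptive and the trial plans no formal inference. That limits the consequence, but the formula still does not do its job.

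**Conclusion.** The concern holds. The two rules cannot both be correct under any one event window. Under the only window the SAP states for adverse event summaries, Rule 1 is 40 (Q3W) or 54 (QW) days short per subject and the rates are too high.

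For Q3W, the main case because "the Q3W dosing regimen is the intended regimen for Part 2", the upper bound on inflation is 1.21-fold at T = 168 and 1.63-fold at T = 42. For QW it is 1.31-fold and 2.10-fold. The mixed cases shown run from 1.05-fold to 1.74-fold. These sizes rest on the assumed values of T, the assumed 30 days of follow-up under Rule 2, and on reading on-treatment as the SAP 7.6 window. The 39- and 53-day steps need only the assumption that the last known alive date is the end of follow-up.

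One descriptive exposure-adjusted table is affected. The primary incidence endpoint and the decision rules do not use this denominator. It should be corrected before database lock, because the SAP followed exactly would give inconsistent rates.

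**What to change.** State in SAP 7.6.5 that the events counted are those in the SAP 7.6 window, and end person-time at the same point for both regimens:

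- **Off treatment:** min(last dose + 60 days; last known alive date or, if earlier, end of adverse event follow-up or data cut-off) − first dose + 1.
- **Still on treatment:** last known alive date (or data cut-off) − first dose + 1, as now, with no 60-day cap.

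This gives T + 60 at d = 59 and T + 61 from d = 60 onward, so the step disappears and the regimens are treated alike. If the team really intends duration of therapy, the consistent alternative is to keep Rule 1, cut Rule 2 off at the same point and restrict the events to match; the SAP must then say so. The 60 days should be tied to the event window in the text: Protocol 5.3 and 8.3.1 use 100 days for combination therapy, which the current SAP does not cover.

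The cost is one sentence, one formula and the matching program edit, with no new data. The reported rates will be lower than under the present text.

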**Summary:**

The following summary tables will be provided:

- Total number and rate (exposure adjusted) of occurrences for all AEs occurring in at least 5% of the subjects treated in any dose + dose regimen group.

**Listing:**

- Unique instances of all AEs, ie, after duplicates have been eliminated and overlapping and contiguous occurrences of the same event (ie, same PT) have been collapsed.

**7.6.6 Adverse Events of Special Interest**

Not applicable at the time of the development of this statistical analysis plan.

**7.6.7 Clinical Laboratory Evaluations**

Clinical laboratory data will be first analyzed using International System of Units (SI). Analyses will be repeated using US conventional units.

**Summary:**

The number (%) of subjects with the following will be summarized by treatment and overall, if appropriate, using the worst CTC grade on-treatment per subject.

- Post-baseline grade
- Grade change from baseline
- Descriptive statistics of laboratory test result and their changes from baseline by treatment and study day

**Listing:**

A by-subject listing of these laboratory parameters will be provided. Laboratory abnormality criteria and laboratory results outside of normal range will be listed.

**7.6.7.1 Abnormal Hepatic Test**

**Summary:**

The number of subjects with the following laboratory abnormalities from on-treatment evaluations will be summarized by dose and dose regimen:

- ALT or AST > 3 x ULN, > 5 x ULN, > 10 x ULN and > 20 x ULN
- Total bilirubin > 2 x ULN
- Concurrent (within 1 day) ALT or AST > 3 x ULN and total bilirubin > 2 x ULN

**Figure:**

- Scatter plot of Total bilirubin peak vs AST peak
- Scatter plot of Total bilirubin peak vs ALT peak

On-treatment peak total bilirubin and on-treatment peak AST/ALT needs to happen on the same day of liver testing.

**Listing:**

A by-subject listing of these specific abnormalities will be provided.

**7.6.7.2 Other Labs of Interest**

A by-subject listing of these specific labs of interest, e.g. related to neutropenia (neutrophil count) and thrombocytopenia (platelet count) will be provided with flags for abnormal value.

Additional plots may be provided to explore potential effects of changes over time in these lab parameters.

### **7.6.8 ECG**

#### **Summary**

- ECG measures
  - The frequency distribution of subjects' maximum recorded post-dose QTcF, PR, QRS and  $\Delta$ QTcF will be tabulated by treatment and summarized for the following ranges:
    - ◆ For QTcF:  $QTcF \leq 450$  msec,  $450 \text{ msec} < QTcF \leq 480$  msec,  $480 \text{ msec} < QTcF \leq 500$  msec,  $QTcF > 500$  msec
    - ◆ For PR:  $PR \leq 200$  msec,  $PR > 200$  msec
    - ◆ For QRS:  $QRS \leq 120$  msec,  $QRS > 120$  msec
    - ◆ For  $\Delta$ QTcF:  $\Delta$ QTcF  $\leq 30$  msec,  $30 \text{ msec} < \Delta$ QTcF  $\leq 60$  msec,  $\Delta$ QTcF  $> 60$  msec

#### **Figure:**

- ECG measures
  - Scatterplot and regression of  $\Delta$ QTcF on active ADC, [REDACTED] and unconjugated tubulysin concentrations, respectively.

#### **Listing:**

- ECG measures
  - Individual QTcF, PR, QRS or  $\Delta$ QTcF values will be listed.
- ECG abnormalities

### **7.6.9 Vital Signs and Other Safety Evaluation**

#### **Summary:**

- Vital signs

#### **Listing:**

- Vital signs
- Diagnostic procedures
- Medical treatment procedures

### **7.6.10 Immunogenicity**

#### **Summary:**

The number (%) of subjects with the following anti-drug responses will be reported by dose, if applicable, and overall.

- Baseline ADA Positive
- ADA Positive
  - Persistent Positive
  - Only the Last Sample Positive

- Other Positive
- ADA Negative

**Listing:**

- All collected immunogenicity will be listed with flags indicating baseline positive sample, ADA positive sample or ADA negative sample, and information regarding specificity to the antibody or unconjugated tubulysin if such data are available.

## 7.7 Pharmacokinetics

PK parameters for the total antibody, [REDACTED] active ADC, [REDACTED] and unconjugated tubulysin will be calculated using noncompartmental analysis. All available plasma/serum concentration-time data from subjects who receive BMS-986148 will be reported. All available derived PK parameter values will be included in the PK dataset and reported, but only subjects with adequate PK profiles will be included in summary statistics and statistical analysis.

PK analysis will be provided separately for each of the above analytes. In general, summary statistics will be tabulated for the pharmacokinetics parameters by dose, dose regimen, and study day for each select analyte. To assess the attainment of steady state geometric mean Ctrough values will be plotted versus study day by dose and dose regimen.

Exploratory assessment of dose proportionality for total antibody, [REDACTED] and unconjugated tubulysin will be performed based on the power model described by Gough et al.

$$\text{PK Parameter} = A * \text{Dose}^{\beta},$$

which be estimated by the simple linear regression of the natural log of the PK Parameter (Cmax, AUC(TAU)) on the natural log of Dose:

$$E[\log(\text{PK Parameter})|\text{Dose}] = \alpha + \beta * \log(\text{Dose}).$$

A slope ( $\beta$ ) equal to 1 would indicate perfect dose proportionality. For each PK parameters (Cmax, AUC(TAU)), the point estimates and 90% CI of the slopes will be provided. Note that dose proportionality analysis may not be performed if there are two few different doses under some dose regimen, e.g., for the QW dosing for three weeks with one week off.

[REDACTED]

A population pharmacokinetic analysis may be conducted, which would be presented in a separate report.

